Study Title: Imaging Cardiac Amyloid Burden: A pilot Study Using F-18 Florbetapir Positron Emission Tomography

NCT Number: NCT01683825

Document Date: January 2018

Analytical Plan

Study Objective(s)

Specific Aim: The *primary aim* of this pilot study is to determine whether amyloid deposits in the heart can be measured non-invasively by F-18 florbetapir (Trade Name: Amyvid) positron emission tomography (PET) in 30 individuals with documented cardiac amyloidosis and in 15 volunteers without cardiac amyloidosis.

A secondary aim of this study is to determine reproducibility of F-18 florbetapir uptake in the myocardium.

Study groups:

Subjects with cardiac amyloidosis and control subjects without cardiac amyloidosis.

Imaging Methods

In this pilot feasibility study, F-18 florbetapir was used to image myocardial amyloid deposits. F-18 florbetapir PET/CT images were acquired in a dynamic mode and reconstructed into static images. Visual assessment and SUV of myocardial uptake of F-18 florbetapir was performed on static images from 4 minutes to 30 minutes. The left ventricular global myocardial F-18 florbetapir images were reviewed in the standard radiological and cardiac imaging planes. We used PMOD software to measure global left ventricular standardized uptake value (SUV) of F-18 florbetapir using SUV mean (SUVmean).

Statistical Methods

This is a pilot feasibility study using F-18 florbetapir to image myocardial amyloid deposits. Mean and maximal myocardial uptake of F-18 florbetapir will be estimated in the subjects with diagnosed cardiac amyloid. Mean liver to heart ratio will be estimated.

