Cardiac involvement is a common manifestation of light-chain (AL) amyloidosis and is a ubiquitous and predominant finding in senile systemic amyloidosis (SSA). In AL amyloidosis, it is a major determinant of treatment options and prognosis² and in SSA, it is almost invariably the cause of death. In amyloidosis with cardiac involvement, the coronary microvasculature is subject both to extrinsic compression and to direct deposition of amyloid within the vessel wall. The resultant abnormalities in coronary microvascular perfusion (the small vessels of the heart) may be responsible for the high incidence of sudden death in AL amyloidosis⁴ and the high treatment-related mortality in AL patients with cardiac involvement undergoing high-dose chemotherapy with autologous stem cell transplant. Microvascular ischemia can be diagnosed noninvasively using standard rest and stress nuclear imaging techniques utilizing isotopes such as sestamibi or thallium, or N-13 ammonia or rubidium-82. However, these tests involve use of stress testing with vasodilator stress which is not well tolerated by patients with amyloidosis particularly those with neuropathy. At this time, although we can measure myocardial ischemia as an effect of myocardial amyloid deposition and/or toxicity, we do not have the capability to assess myocardial amyloid burden directly.

A newly developed radiotracer F-18 labeled florbetapir has been recently approved by the FDA for imaging beta amyloid in the brain of patients with Alzheimer's' disease. 6-10 If these F-18 labeled florbetapir binds to cardiac amyloid protein, then the potential to quantify myocardial amyloid burden is available. Assessment of myocardial amyloid burden holds the potential for better understanding the nature of cardiac dysfunction and can potentially help assess response of therapy specifically targeted against amyloid production. Data from this pilot study will aid the principal investigator in designing a more definitive larger prospective multicenter study of cardiac amyloidosis, a rare disease, using F-18 florbetapir to estimate myocardial amyloid burden and follow response to therapy with novel therapeutic agents.

b) Previous studies leading up to or supporting the proposed research

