F-18 florbetapir has been studied in multiple clinical trials to image beta-amyloid deposition in the brain of subjects with Alzheimers' disease. Florbetapir F-18 has been well tolerated in studies of more than 2000 human subjects. Biodistribution studies in humans revealed predominantly hepatobiliary excretion. The tracer clears rapidly from the blood pool in about 20 minutes (6). This radiotracer has been recently approved for clinical imaging of brain amyloid in subjects with suspected Alzheimer's

disease. In this pilot study, F-18 florbetapir images will be acquired immediately after injection and at 90 minutes after injection to study radiotracer bio-distribution and understand the optimal time for imaging.

Preliminary studies using C-11 labeled PiB (another agent used to image beta-amyloid in the brain of patients with Alzheimer's disease)¹¹ show that this tracer can be taken up by cardiac amyloidosis (unpublished data in abstract form from Uppsala University, Sweden). However, this tracer is produced by a cyclotron and has a short half-life of 20 minutes; hence it can only be used in sites with a cyclotron on site, limiting its applicability for multicenter studies. We propose to test a longer half life tracer, F-18 florbetapir in a pilot study to evaluate their potential utility to image cardiac amyloidosis. If this agents works, that will enable us to plan a large multicenter study of this rare disorder allowing us the potential to detect preclinical disease as well as follow response to therapy.

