Amyloid related heart disease is associated with LV wall thickening due to infiltration; however, this myocardial wall thickening is not definitively distinguishable from left ventricular myocyte hypertrophy from increased afterload to the heart from hypertension or aortic stenosis. Typically myocardial or other tissue biopsy with typical echo features of amyloidosis is required for confirmation of amyloidosis. This pilot study is designed to understand whether we can measure cardiac amyloid burden using a specific radiotracer targeted against amyloid protein (F-18 florbetapir). The longer half-life (120 minutes) of F-18 florbetapir, makes it a more attractive tracer for conducting a multicenter clinical study, since this radiotracer can be delivered to sites without an onsite cyclotron. At this point it is unknown if F-18 florbetapir will bind to either AL or TTR amyloid protein or to both of them or to neither of them. Hence, we would like to study 15patients with AL, 15 patients with TTR amyloidosis and 15 volunteer subjects without amyloidosis [including 10 elderly subjects with clinical heart failure with preserved ejection fraction (HFpEF)] to understand these differences if any. We also seek to understand if the signal to noise ratio of the circulating amyloid protein in the blood pool (AL amyloid disease) allows for good differentiation of myocardial amyloid uptake.

The purpose of the proposed research study is to examine in detail, using quantitative PET, myocardial F-18 florbetapir uptake in cardiac amyloidosis in order to better understand mechanisms of heart damage in this disease. The following specific aim is proposed:

II. SPECIFIC AIM:

The *primary aim* of this pilot study is to determine whether amyloid deposits in the heart can be measured non-invasively by F-18 florbetapir (Trade Name: Amyvid) positron emission tomography (PET) in 10 individuals with documented cardiac amyloidosis and in 5 individuals without cardiac amyloidosis.

A secondary aim of this study is to determine reproducibility of F-18 florbetapir uptake in the myocardium.

III. SUBJECT SELECTION

a) Inclusion and Exclusion Criteria:

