During the course of this research study, we will draw a total of 35-40cc_of blood. This includes 10 cc of blood for oxidative stress markers (if subject provides additional consent), 15 cc of blood for florbetapir metabolite analysis, 10 cc of blood for metabolomics and mito DNA measures (if subject provides additional consent), 5 cc for pregnancy test (in individuals who need them). Pregnant women and breastfeeding women cannot take part in this research study.

Serum F₂-isoprostane and Peroxynitrite— 10 cc of blood samples will be collected in EDTA tube before the PET/CT scan of Study Visit 2 to measure serum markers of oxidative stress. F₂-isoprostanes will be measured in [name] laboratory using serum isolated from whole blood collected with EDTA and stored at -80°C using immunoassay (8-isoprostane EIA kit, Cayman Biochemical). If needed, findings can be confirmed using mass spectroscopy. Nitrotyrosine levels will be measured in serum that is stored at -80°C by immunoassay (Nitrotyrosine EIA kit, Oxis).

Serum metabolomic analysis—10 cc of blood samples will be collected in EDTA tubes before the PET/CT scan of Study Visit 2 for metabolomic and mitochondrial DNA analyses.

Urine Samples: 24 hour urine sample will be collected. The urine samples will be deindentified by a study subject code and used to extract light chains that will be infused into zebra fish with or without pretreatment with rapamycin to study cardiac function and survival.

VI. BIOSTATISTICAL ANALYSIS

This is a pilot feasibility study using F-18 florbetapir. Mean myocardial uptake will be estimated in the subjects. Mean liver to heart ratio will be estimated.

VII. RISKS AND DISCOMFORT

Time: Participation in this trial entails a rest F-18 florbetapir PET/CT scan. The total time spent for the study procedures is approximately 2 hours.

Intravenous line insertion: Possible side effects intravenous line insertion are pain, bruising, or infection where the needle entered the skin. Some people faint or get dizzy during insertion of the intravenous line.

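### The primary aim asks whether cardiac amyloid can be measured, but the planned summaries include no comparison with controls, no interval and no result defined in advance as negative

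*SAP*

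**What the plan says.** The SAP (Study Objective(s)) states the primary aim as "to determine whether amyloid deposits in the heart can be measured non-invasively by F-18 florbetapir", "in 30 individuals with documented cardiac amyloidosis and in 15 volunteers without cardiac amyloidosis". The Protocol synopsis has the same aim and sizes. The Protocol's Specific Aim section still gives 10 and 5 for the same aim, which needs reconciling.

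Protocol, Background and Significance b), says "it is unknown if F-18 florbetapir will bind to either AL or TTR amyloid protein or to both of them or to neither of them". It gives this uncertainty as the reason for studying 15 AL patients, 15 TTR patients and 15 volunteers. The same section looks ahead: "If this agents works, that will enable us to plan a large multicenter study of this rare disorder". Background a) is softer: "Data from this pilot study will aid the principal investigator in designing a more definitive larger prospective multicenter study".

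The analysis text is short. SAP, Statistical Methods, and the Protocol synopsis: "Mean and maximal myocardial uptake of F-18 florbetapir will be estimated in the subjects with diagnosed cardiac amyloid", followed by a mean liver-to-heart ratio. Protocol VI: "Mean myocardial uptake will be estimated in the subjects. Mean liver to heart ratio will be estimated". The SAP's imaging text names global left ventricular SUVmean as the quantity measured. Protocol V defines a 0 to 3 visual score on which 0 is normal. No statistical section uses the score.

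**The concern.** The aim is worded as a question with a yes or no answer, and the background splits it by amyloid type. The planned output is a set of averages with nothing to set them against. SUV is a tissue concentration scaled to the dose given, so blood pool and non-specific uptake give a value above zero in any heart. The Protocol itself asks whether myocardial signal can be told apart from the blood pool. The controls are what would separate specific uptake from that background, yet two of the three statistical texts leave them out of the uptake estimates, and the third makes no comparison.

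What is at stake is how the result will be read. Without a stated comparison, the standard for saying that the tracer detects AL, TTR or both can be settled after the values are known. The answer that it binds neither has no result assigned to it in advance.

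**Working it through.** The plan has no sample-size or precision figure to reproduce. Only the group arithmetic can be checked: 15 + 15 + 15 = 45, which agrees with the enrolment cap.

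**Step 1: can the planned output separate the four answers?** Let c be the mean SUV without specific binding. The controls estimate c. Let m_AL and m_TTR be the means in the two types. The four answers are statements about two differences, m_AL − c and m_TTR − c. The SAP lists two study groups, amyloid and control, and does not say that uptake will be reported by type. With 15 of each type, a single amyloid mean is (m_AL + m_TTR)/2. For any lift δ:

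- AL only, lift 2δ: (c + 2δ + c)/2 = c + δ
- TTR only, lift 2δ: (c + c + 2δ)/2 = c + δ
- both, lift δ each: (c + δ + c + δ)/2 = c + δ
- neither, with a background level of c + δ: also c + δ

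One amyloid mean fits all four answers. Reporting by type would separate AL only from TTR only. It still could not separate both from neither, because c is not estimated. If Protocol VI is read as covering all subjects, c is estimated, but nothing states how the means are to be compared or how uncertain the difference is.

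**Step 2: what would the missing comparison deliver?** Inputs: 15 per type and 15 controls (Protocol synopsis). Assumptions, because the documents give no SUV, SD or effect size: normal SUV and equal SD, with differences expressed in SD units. With equal groups and equal SD, the Welch interval is close to the equal-variance one used here.

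Standard error of a difference = √(1/15 + 1/15) = 0.365 SD; df = 28.

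- 95% half-width: 2.048 × 0.365 = 0.75 SD
- 97.5% half-width: 2.368 × 0.365 = 0.86 SD

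**Step 3: how often would an interval lie above 0?** The probability for one type is P(T > critical t), where T is noncentral t with 28 df and noncentrality d/0.365.

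| True difference d | Noncentrality | 95% interval | 97.5% interval |
|---|---|---|---|
| 0.5 SD | 1.37 | 0.26 | 0.17 |
| 1.0 SD | 2.74 | 0.75 | 0.65 |

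A probability of 0.80 needs a true difference of about 1.06 SD with the 95% interval and 1.18 SD with the 97.5% interval. The planned size can therefore show a large difference in each type, but not a modest one.

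**The case against.** The strongest reply is that this is a pilot feasibility study whose quantities are to be estimated. Such a study need not have an alpha, a power calculation or a hypothesis test. That stands, and the absence of those items is not the defect. A difference with its interval is itself estimation, and it is what the plan lacks.

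Three stronger readings are tempting, and the documents do not support them.

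- A reader might infer that no result could ever count as failure. Protocol V labels a visual score of 0 as normal, so scores of 0 throughout both amyloid groups would be recognised as no uptake, and the background openly allows for binding to neither protein. What holds is narrower: no result is prespecified as negative.
- A reader might infer a formal go/no-go gate for the multicentre study. The sentence about the agent working is background planning language, and the SAP has nothing like it.
- A reader might assign the plan a false-positive rate by supposing that success means an amyloid mean above the control mean. The plan states no such rule, so that figure would describe an invented rule. How far candidate rules disagree also depends on the true effect: they diverge at 1 SD, but at 3 SD most of them agree.

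Timing also counts against a strict rule. The SAP is dated January 2018 and describes imaging in the past tense, while the Protocol's enrolment period runs from February 2013 to October 2018. This does not show that groups had been compared, but it makes a cleanly prespecified pass mark doubtful.

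**Conclusion.** The point holds in limited form. Carried out exactly as written, the SAP yields point summaries that cannot answer the primary aim or separate the four binding outcomes that the Protocol names. The missing piece is a comparison of each amyloid type with controls, with an interval and a stated reading. That Step 1 result needs no distributional assumption; it follows from the groups and quantities that the texts list.

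The precision figures do rest on assumptions: 15 per group, normal SUV and equal SD. On that basis each type's difference would be known to about ±0.75 SD at 95%, or ±0.86 SD at 97.5%. The documents give no ground for a particular SUV cut-off, and none is needed. A mean difference above 0 would show uptake above controls on average, not that individual patients can be told apart, so individual values belong beside it.

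**What to change.** In SAP Statistical Methods, repeated in Protocol VI:

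- Name left ventricular SUVmean as the primary measure.
- For AL and TTR separately, report the difference in mean (amyloid minus control) with a Welch confidence interval at a stated level. Use 95%, or 97.5% if the two statements are to share 5%. Show individual values by group.
- Conclude uptake above controls for a type only if its interval lies above 0. Otherwise report that uptake in that type was not shown to differ from controls.
- Treat maximal uptake, the liver-to-heart ratio and the visual score as supportive.
- State the expected precision and its assumptions.
- Disclose whether SUVs by group had been seen when this text was written. If they had, word the aim as estimation.

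Do not make planning of the multicentre study formally conditional on the result. A wide interval from 15 patients is weak ground for such a bar.

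The cost is a few sentences, with no new patients, scans or readers. The downside is that a true difference of 0.5 SD in a type would be reported as not shown about three times in four with the 95% interval (1 − 0.26 = 0.74), and more often with the 97.5% interval (1 − 0.17 = 0.83).

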The main goal of this pilot study is to prospectively study myocardial amyloid deposition using quantitative F-18 florbetapir PET/CT in 30 subjects with cardiac amyloidosis and 15 volunteers without cardiac amyloidosis including, 10 elderly subjects with clinical heart failure with preserved ejection fraction (HFpEF) over a period of 2 years. A total of 10 AL and 10 ATTR amyloid patients will undergo a repeat F-18 florbetapir PET scan within a month of the initial study (next day to one month). Subjects will be eligible if they meet all of the following inclusion criteria and none of the exclusion criteria:

Main Selection Criteria

Subjects will be eligible if they meet all of the following inclusion criteria and none of the exclusion criteria:

Inclusion criteria for amyloid subjects:

- Age > 18 years
- Biopsy proven amyloidosis outside the heart with typical echocardiographic appearance of cardiac involvement, or a positive cardiac biopsy.
- Diagnosis of AL amyloidosis by standard criteria (evidence of plasma cell dyscrasia with appropriate tissue staining for AL) OR
- Diagnosis of TTR amyloidosis (no evidence of plasma call dyscrasia and positive TTR staining of amyloid in tissue biopsy)
- Able and willing to provide informed consent to participate in the study procedures
- 10 subjects with HFpEF age >70 years will be included in the control group.

Exclusion criteria for both amyloid and volunteer subjects:

- Pregnancy
- In the 10 subjects with HFpEF age >70 years, prior coronary artery disease, coronary revascularization or severe valvular heart disease

b)	Source of subjects and recruitment methods
Pat	tients will be recruited from the advanced heart failure group at the Hospital and from the
car	diology practice of Dr, an expert in cardiac amyloidosis. Among them, stable and eligible
pat	tients meeting all inclusion and exclusion criteria will be invited to participate in this study and those
wh	o provide informed consent will be enrolled. Majority of the subjects with be enrolled from the clinica
pra	actice of Dr, an expert in Cardiac amyloidosis.
IV.	SUBJECT ENROLLMENT
a)	Methods of enrollment including procedures for patient registration and or randomization
	The following recruitment methods will be used:
	• This is a pilot study of subjects with a rare disease. Typically these subjects are well characterized
	clinically in terms of their evaluation. Majority of the subjects will be recruited from the clinical

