- b. This screening visit will take about 1 hour. The research study team will ask the subject questions about medical history to make sure that the subject qualifies for this study. Pregnancy is not allowed due to the unknown risks radioactivity may have on the mother or the unborn baby from the beginning of the study period through the end of the study.

b. Study visit 2

The screening and study visit 1 can be conducted on the same day. Study visit 1 is for the performance of the rest F-18 florbetapir imaging study, 6-minute walk test, and 24 hour urine collection as described below. This visit will take about 2 hours, preparation time of 30 minutes, scan time of one and a half hours, and 6 minutes of walking. A blood pregnancy test will be performed on the day of the PET scan in women with child bearing potential, using 5 cc / one teaspoonful of blood. The research procedures will include intravenous injection of 10 mCi a radiotracer agent (F-18 florbetapir) followed by a ninety minute image acquisition. Three teaspoonfuls of blood will be drawn for florbetapir metabolite analyses.

b. Study visit 3

The study visit 3 can be conducted on the next day or within the next 30 days. Study visit 3 is for the performance of the rest F-18 florbetapir imaging study as described below. This visit will take about 2 hours, preparation time of 30 minutes, and scan time of one and a half hours. A blood pregnancy test will be performed on the day of the PET scan in women with child bearing potential, using 5 cc / one teaspoonful of blood. The research procedures will include intravenous injection of 10 mCi a radiotracer agent (F-18 florbetapir) followed by a ninety minute image acquisition. Two teaspoonfuls of blood will be drawn for florbetapir metabolite analyses.

Detailed Description of F-18 florbetapir PET/CT Methods: The proposed research will utilize the resources of the Cardiovascular Imaging center at Brigham and Women's Hospital, Boston MA. Specifically, PET imaging will be performed on a state-of-the-art 64 slice cardiac PET/CT unit.

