Before the test: All patients will receive written instructions to have a light breakfast such as toast or cereal with coffee, tea or juice prior to their scan and to bring all their medications (including prescription, over the counter, dietary supplements, herbal and vitamins) with them. Upon arrival for the test, all patients are given a written questionnaire about allergies and possibility of pregnancy. Women of child bearing age will undergo a blood pregnancy test prior to the injection of F-18 florbetapir, as per laboratory protocol. Written informed consent for the study is checked and IV line inserted and the patient brought into the PET/CT room for imaging.

F-18 florbetapir PET/CT image acquisition:

A typical image acquisition protocol will include a CT scout image (10 mA, AP scout) to localize the heart followed by a CT transmission image (10 mA, 120 KVp, non-gated, free tidal breathing) for correction of photon attenuation by soft tissues, followed by injection of 10 mCi of F-18 florbetapir. F-18 florbetapir images are acquired in a 3D list mode for 90 minutes. Rest emission images will be unlisted for analysis into a static file, a gated file and dynamic image frames. The same protocol will be used for study visit 3. 2.5 cc blood samples will be drawn for metabolite analyses at 6 time points for the first 60 minutes.

Interpretation and quantification of F-18 florbetapir images:

The myocardial F-18 florbetapir images will be processed and viewed in the standard cardiac imaging planes. Visual assessment of relative myocardial uptake of F-18 florbetapir will be performed and scored using a 0-3 scale (0=normal, 1= mild uptake, 2= moderate uptake, 3=significant uptake). Myocardial uptake of F-18 florbetapir will be quantified using software on the Hermes system (image viewing station). Also, specific uptake values of the radiotracer in the myocardium will be computed.

6-minute walk:

Subjects will be asked to walk back and forth along a flat corridor between two markers set a distance apart at their own pace. The test takes 6 minutes and the distance that is walked will be measured.

Total Amount of Blood Drawn:

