Radioactive imaging agents may have the following side effects: The radiation exposure to the subjects from the use of F-18 florbetapir is calculated to be at 7.93 mSv that is equivalent to about 19 31 months of background radiation in Boston. In the 20 subjects undergoing reproducibility evaluation, the scan will be repeated in another day, with additional radiation exposure from the use of F-18 florbetapir of 7.93 mSv for a total study related radiation dose of (15.86 mSv). Other side effects include: headache, musculoskeletal pain, nausea and fatigue. Radiation exposure associated imaging is within acceptable safety standards as set forth by the FDA. Radiation may cause physical or genetic damage to a fetus, so subjects that are pregnant or breast feeding will be excluded. A pregnancy test will be performed prior to enrolling patients with childbearing potential.

Risks from 6-minute walk test: The risks and discomforts associated with this procedure are very similar to those that subjects would incur with exercising on their own.

In addition to the risks or discomforts listed above, the study drug and procedures may have unknown side effects. There is always the possibility that subjects will have a reaction that is currently not known or not expected. All drugs can cause an allergic reaction that, if not treated promptly, could be life-threatening. Symptoms of such a reaction are: throat tightness, itching, hives, wheals, vomiting, difficulty breathing or turning blue.

VIII. POTENTIAL BENEFITS

No direct benefit is anticipated to individual subjects. The results of this study may benefit society through evaluation of the diagnostic utility of a novel radiotracer for directly imaging myocardial amyloid burden in subjects with cardiac amyloidosis.

IX. MONITORING AND QUALITY ASSURANCE

Subject safety will be ensured by strict adherence to inclusion and exclusion criteria and close monitoring. Subjects that experienced serious adverse events during the study will be removed from the study and followed up, but no other study procedures will be performed. This study does not involve treatment and hence a data safety monitoring board.

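### Must the plan name a test-retest statistic for the 20 repeat scans, given that reproducibility is a secondary aim?

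*SAP*

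**What the plan says.** Reproducibility of myocardial uptake is the secondary aim in the protocol Synopsis, in protocol section II (Specific Aim) and in the SAP: "A secondary aim of this study is to determine reproducibility of F-18 florbetapir uptake in the myocardium".

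The design provides for it:

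- Protocol section III (Subject Selection), as in the Synopsis: "A total of 10 AL and 10 ATTR amyloid patients will undergo a repeat F-18 florbetapir PET scan".
- Protocol section V (Study Procedures), on timing: "The study visit 3 can be conducted on the next day or within the next 30 days". The visit includes a second tracer injection and a 90-minute acquisition, and the acquisition protocol is the same as for the first scan.
- Protocol section VII (Risks and Discomfort), on purpose: "In the 20 subjects undergoing reproducibility evaluation, the scan will be repeated in another day". The second scan adds 7.93 mSv, for a total of 15.86 mSv.

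The statistical text is short. The SAP Statistical Methods and the Synopsis both say: "Mean and maximal myocardial uptake of F-18 florbetapir will be estimated in the subjects with diagnosed cardiac amyloid". They then add the mean liver-to-heart ratio. Protocol section VI (Biostatistical Analysis) says: "Mean myocardial uptake will be estimated in the subjects. Mean liver to heart ratio will be estimated". None of the three mentions the second scan.

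**The concern.** Patients accept a second radiation exposure for a named aim, and no statistical section says how the two scans will be compared. Estimating mean uptake does not answer the question, because two group means can agree while individual pairs differ widely.

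An unstated method also leaves room for choice after the data are seen. The open choices are the statistic (within-subject SD, coefficient of variation, intraclass correlation, limits of agreement), the uptake measure, and whether AL and ATTR are pooled. Protocol section I (Background and Significance) says the pilot is meant to inform a larger study that follows response to therapy. Such a design would probably need a figure for test-retest error, although that is an inference. If the choice were made badly, the later study could inherit a flattering figure.

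**Working it through.** **1. The plan's own figures.** 10 AL + 10 ATTR = 20 repeat scans, which agrees with section VII. 2 × 7.93 mSv = 15.86 mSv, which also agrees.

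**2. Count of between-scan estimators.**

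| Section | Quantities listed | Between-scan estimators |
|---|---|---|
| Protocol Synopsis, Statistical Methods | mean and maximal uptake, liver-to-heart ratio | 0 |
| Protocol VI, Biostatistical Analysis | mean uptake, liver-to-heart ratio | 0 |
| SAP, Statistical Methods | mean and maximal uptake, liver-to-heart ratio | 0 |

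**3. What is already fixed without an estimator.** The protocol sets the patients and their types, the interval (next day to 30 days), the acquisition and the purpose. The SAP Imaging Methods set the SUV measure: global left ventricular SUVmean, static images from 4 to 30 minutes, PMOD software. Only the summary statistic remains open, together with whether maximal uptake or the liver-to-heart ratio is summarised as well.

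**4. How much the choice of statistic matters.** Let d be the scan 2 minus scan 1 difference in one patient.

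- Within-subject SD: s_w = SD(d)/√2.
- Repeatability coefficient: 1.96 × √2 × s_w = 2.77 × s_w = 1.96 × SD(d).
- Limits of agreement: mean(d) ± 1.96 × SD(d).

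The repeatability coefficient equals the half-width of the limits of agreement. These three are rescalings of one quantity, so choosing among them changes the presentation and not the finding.

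The intraclass correlation is different, because it equals between-subject variance / (between-subject + within-subject variance). The documents give no coefficients of variation. Assume 10% within subject:

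- Between-subject 20%: 0.04 / (0.04 + 0.01) = 0.80.
- Between-subject 50%: 0.25 / (0.25 + 0.01) = 0.96.

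Measurement error is the same in both cases. An intraclass correlation reported alone would therefore be a weak answer.

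**5. Whether naming the statistic improves precision.** The 95% interval for s_w, as a multiple of its estimate, is √(df/χ²) at the 97.5% and 2.5% points.

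- One type, 10 pairs, 9 df: 0.69 to 1.83.
- Both types with type-specific mean differences, 20 pairs, 9 + 9 = 18 df: 0.76 to 1.48.

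These follow from the number of pairs. They would be identical if the SAP already contained a full reproducibility section, so they do not measure the omission.

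**6. Whether an addition could still be prospective.** The SAP is dated January 2018 and describes imaging in the past tense. The protocol's first page has enrolment running to October 2018, the Synopsis gives a planned period of 2Q2013 to 2Q2017, and section III speaks of 2 years. If the Synopsis period held, every scan came before the SAP and any added text would be wholly post hoc. The documents do not settle which applies.

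**The case for a change.** The strongest case for a change is that pilot status explains the lack of a power calculation but not the lack of any estimator for a named aim. Estimation is what a pilot is for, and 20 patients bear a second exposure for it. The remedy would cost a sentence and no new scan.

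Part of this stands. The omission is real and neither redaction nor PDF conversion explains it. A named statistic would be better practice, and the caution about relying on an intraclass correlation alone is sound.

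The rest does not carry the point to a required change:

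- It is too strong to say that the second scan has no planned use. Section VII assigns it to reproducibility evaluation, and only the statistic is unspecified.
- Preferring the within-subject SD over a coefficient of variation, or results by type before pooled results, is a matter of taste. Both groupings can be computed from the same pairs. Analysts can also check whether error grows with uptake and use a relative scale if it does.
- Protocol section V names Hermes for quantification, whereas the SAP names PMOD. That is a separate clerical inconsistency. Nothing in the documents suggests that the two scans of one patient were processed differently, so a loss of reproducibility from mixed software is conjecture.

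**Conclusion.** The concern describes a true gap, but not one that requires the plan to change. Its size is 20 second scans with no named paired analysis. No stated number or rule is wrong, no hypothesis test or acceptance threshold depends on the missing text, and the primary aim is unaffected. The paired data, the purpose and an operational uptake measure are all specified, so a competent analyst would fill the gap with a standard test-retest summary.

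This rests on two assumptions: that both scans of each patient are measured in the same way, and that an error-scale statistic is reported instead of an intraclass correlation alone. The 10%, 20% and 50% coefficients of variation are illustrations and do not come from the documents. Whatever is reported, 10 pairs per type will give wide intervals, and two scans up to 30 days apart cannot separate real short-term change from measurement error. Naming a statistic in the SAP would alter neither limit.
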